9.4. Premature Withdrawal and Missing Data

9.4.1. Premature Withdrawal from ‘IP only’ Prior to Week 52

Subjects who discontinue IP but do not withdraw from the study will continue the visit schedule through Week 52 and will be contacted annually for Years 2 through 5 to assess mortality and malignancy.

- All data collected through Week 52 post withdrawal from IP will be included in summaries unless otherwise specified.
- Annual assessment of mortality and malignancy will be included in the summaries of Year 2 to 5 (to be detailed in a separate RAP).

9.4.2. Withdrawal from Study Prior to Week 52

For subjects who withdraw from the study prior to Week 52, an attempt will be made to assess mortality and occurrence of malignancy (including NMSC) at Week 52 and annually for Years 2-5.

- For subjects who withdraw from the study, all data reported on the database will be used in the summaries through Week 52 unless otherwise specified.
- For subjects that withdraw early from Year 1 of the study, Week 52 mortality information will be collected if allowed by individual subject’s legal consent status. This includes the potential use of a third party to aid sites in identifying information available from public sources.

9.4.3. Missing Data

Adverse Events (AESIs, Serious Adverse Events) and Concomitant Medications

Missing Dates

Element	Reporting Detail
General	Partial dates will be displayed as captured in subject listings.
Concomitant Medications	
 • Where medication start date (CMSTDT) is completely missing but medication end date (CMENDT) is on or after Day 1, the medication start date (CMSTDT) will be imputed as study treatment start date (TRTSDT). • Where medication start date (CMSTDT) is completely missing and medication end date (CMENDT) is missing and the medication is ongoing (CMONGO = “Y”), the medication start date (CMSTDT) will be imputed as study treatment start date (TRTSDT) and the medication will be considered as ongoing. 
Medication End Date (CMENDT) Missing end dates for concomitant medications will not be imputed, and the medication will be considered ongoing. For corticosteroids, the medication end date will be imputed as study completion or withdrawal date during the ADPRED dataset creation in order for those medications to be included in prednisone summaries. However, if the start date of the medication is greater than the study completion or withdrawal date, the end date will not be imputed.

Adverse Events	The eCRF does not allow for the possibility of missing or partial AE dates (except for missing AE end dates which are allowed if the AE is ongoing).

See Section 9.5.13 for further details on whether AE is considered as treatment-emergent.

Other than described above, missing data will not be imputed unless stated otherwise for an individual endpoint.

A missing category will be added to frequency counts if there is at least one missing record.

Partial Dates

Element	Reporting Detail
Date of Birth	
 • Only year of birth is collected on the eCRF. • Day will be set to 30 and month will be set to JUNE for all subjects.
Concomitant Medications	
Medication Start Date (CMSTDT) Medication start date (CMSTDT) is imputed as study treatment start date (TRTSDT) unless:
 
 • CMENDT is < TRTSDT, whether CMENDT is complete (DD/MM/YY) or partial (some combination of CMENDT day, month or year imputed) OR • The month or month and year of the partial CMSTDT are different from the month and/or year of TRTSDT OR • “Taken prior to study?” is checked. 
If any of the above conditions are met then medication start date (CMSTDT) is imputed with JAN for missing month and 01 for missing day, whatever is applicable.
 
Medication End Date (CMENDT)
 
 • If month and year are present, then: 
 • If the medication started on or after study withdrawal or completion then set to the last day of that month. • If the medication started prior to study withdrawal or completion set to the last day of that month, unless the end month and year are the same as the month and year of the study withdrawal or completion date, in which case set to the study withdrawal or completion. date. • If only year present, then: 
 • if the medication started on or after study withdrawal or completion then set to 31DEC. • if the medication started prior to study withdrawal or completion then set to 31DEC, unless the end year is the same as the year of the study withdrawal or completion date, in which case set to the study withdrawal or completion date.
Date of SLE diagnosis	
 • For records where month and day are missing for diagnosis date, impute with 01 for day and January for month to assume that the duration was the longest possible duration. • For records where the day only is missing for start date, impute with 01 for day to assume that the duration was the longest possible duration.

Element	Reporting Detail
Last known to be alive date	
 For records where month and day are missing for last known to be alive date, impute 01 for day and January for month. For records where the day only is missing, impute 01 for day.

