9.5. Derived and Transformed Data

9.5.1. Baseline

The protocol specifies Day 0 as Baseline/Treatment Start date, but the CDISC standard is to refer to the Baseline/Treatment Start date as Day 1; therefore Baseline/Treatment Start date will be referenced as Day 1 in this document. A table indicating the target study day for each planned visit is in Section 9.5.3.

The baseline value of a variable is defined as the last available value measured prior to dosing on or before the date of first dose (Day 1), unless otherwise specified.

If the last available value occurs on Day 1 but the time of the assessment is not collected, then the assessment will be assumed to be prior to dosing. Noted exceptions to this rule are concomitant medications and AEs; these will be considered as being concomitant and treatment-emergent, respectively, if the start date occurs on the first day of dosing.

However, if time is available for an AE or concomitant medication and the end time is earlier than the start time of first dose of IP, the AE or concomitant medication will not be considered as treatment-emergent or concomitant, respectively.

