9.5.16. Prednisone

All prednisone analyses and summaries will consider SLE-related steroids only but data will also be derived for all indications steroids (SLE and non-SLE) for reference where indicated below.

The following will apply to all derivations in this section unless otherwise stated:

- For steroid use analyses, all steroid dosages are converted to a prednisone equivalent in milligrams; therefore, analyses refer to average daily prednisone dose instead of average daily steroid dose. See [Appendix 4: Prednisone Equivalent Conversion](#) for instructions on converting steroids to prednisone equivalents.
- This appendix will be updated throughout the course of the study to include all corticosteroids taken by subjects and will be finalized prior to the first database release and unblinding.
- For all derivations of the average daily prednisone equivalent dose including baseline, days on which a subject does not have prednisone use recorded will be considered as 0 mg for the day.
- Steroids taken intravenously (IV), intramuscularly (IM), subcutaneously (SC), intradermally, and orally are considered in prednisone dose derivations only.
- All steroids taken on any given day, including overlaps, will be accounted for in calculations of average daily prednisone dose. To achieve this programmatically, each entry is converted to the prednisone equivalent daily dose (see [Appendix 4: Prednisone Equivalent Conversion](#)) and the sum of the prednisone equivalent doses on Day X gives the total prednisone equivalent daily dose on Day X. For example, if two steroids are given on the same day they will be converted to a prednisone equivalent daily dose and then added together to achieve a total for that day.

Steroids used to treat SLE are those with medication type corticosteroid for SLE (SDTM.CM.CMCAT = 'CORTICOSTEROID FOR SYSTEMIC LUPUS ERYTHEMATOSUS').

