9.5.16.1. Average Daily Prednisone Equivalent

Prior to carrying out calculations, each steroid must be converted to its prednisone equivalent and then the daily dose calculated using the frequency factors provided in

[Appendix 4](#): Prednisone Equivalent Conversion. Days on which the subject has no steroid use will be considered as 0mg.

Baseline

At baseline, the average daily prednisone equivalent dose is the sum of all prednisone doses over 7 consecutive days up to, but not including Day 1, divided by 7.

This will be derived for both steroids used to treat SLE and steroids used to treat all indications (SLE and non-SLE) separately. The baseline average daily prednisone dose for all indications will not be reported but will be used to carry out a cross-check against the randomization strata, which were determined by sites based on steroids received for any indication.

Treatment completion average dose

The average daily prednisone dose is the sum of all prednisone doses over 7 consecutive days up to and including the date of treatment completion, divided by 7.

This will be derived for steroids received for SLE only.

9.5.16.2. Average Daily Prednisone Dose during Weeks 40 to 52

The average daily prednisone dose during Weeks 40 to 52 is the sum of all prednisone doses from the day following the Week 40 visit date up to but not including the Week 52 study completion date divided by the number of days between Week 40 visit date and study completion date (study completion date – Week 40 visit date).

For subjects who withdraw from the study prior to the Week 40 visit date, the average daily prednisone dose during Weeks 40 to 52 will be missing.

For subjects who withdraw from the study after the Week 40 visit date, the average daily dose will be calculated as the sum of all prednisone doses from the day after the Week 40 visit date up to and including the date of withdrawal or death, whichever is earlier divided by the number of days between Week 40 visit date and the date of withdrawal or death, whichever is earlier (date of withdrawal or death – Week 40 visit date + 1). If the Week 40 visit is missing for any subject who has not withdrawn or died prior to Week 40, the Week 40 visit date will be imputed as treatment start date + 40 * 7 for this derivation.

This will be derived for steroids received for SLE only.

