12.1. Major Efficacy Analyses

12.1.1. Percent of Subjects with Prednisone Reduction by $\geq 25\%$ from baseline to ≤ 7.5 mg/day during Week 40 through Week 52

Primary Analysis

For this analysis, only steroids used to treat SLE will be included and only subjects with a baseline average daily prednisone dose >7.5 mg/day will be included. See Section 9.5.16.1 for derivation of baseline prednisone dose and Section 9.5.16.2 for derivation of average prednisone use between Week 40 to Week 52.

The percent of subjects whose average prednisone dose has been reduced by $\geq 25\%$ from baseline to ≤ 7.5 mg/day during Weeks 40 through 52 will be compared between belimumab and placebo using a logistic regression model. Independent variables in the model will include treatment group, baseline prednisone dose, and the following

randomization stratification factors per the eCRF: screening SELENA SLEDAI score (≤ 9 vs. ≥ 10), and region. A responder is defined as having a prednisone reduction by $\geq 25\%$ from baseline to ≤ 7.5 mg/day during Weeks 40 through 52.

Any subject who withdraws from the study or adds new immunomodulatory agents used to treat SLE (note that this will include switches) prior to the Week 52 visit will be considered having no steroid reduction.

A summary of the number and percentage of subjects who are responders by treatment group, the treatment difference versus placebo, the odds ratio and 95% CI versus placebo, and a p-value for the odds ratio will also be provided.

Sensitivity Analysis

- To examine the robustness of the results, a sensitivity analysis of the SLE-related steroid reduction will be performed without considering any information related to the use of new immunomodulatory agents (note that this will include switches).

Additional Summaries of Prednisone

- A summary of the number and percentage of subjects with average SLE-related daily prednisone dose ≤ 7.5 mg/day and > 7.5 mg/day at baseline (Day 1) and treatment completion date will be presented for treatment completers.
- The cumulative SLE-related prednisone dose will be derived as described in Section 9.5.16.3. A table of descriptive statistics will be presented including the mean, standard deviation, median, 25th and 75th percentiles, minimum and maximum.
- A listing of cumulative SLE-related prednisone dose will be displayed by treatment and subject.

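### A pre-study steroid with a completely missing start date is set to start on Day 1, just after the baseline window closes, so baseline dose is understated and a subject above 7.5 mg/day can be left out of the major efficacy analysis

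*SAP*

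**What the plan says.** All sections cited are in the Week 52 RAP unless stated otherwise.

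- **Start dates (Section 9.4.3, missing dates).** If the start date "is completely missing but medication end date (CMENDT) is on or after Day 1", it becomes the treatment start date. If the end date is also missing and the drug is ongoing, "the medication start date (CMSTDT) will be imputed as study treatment start date (TRTSDT) and the medication will be considered as ongoing". The corticosteroid rule in the same table deals with end dates only.
- **Partial dates (Section 9.4.3).** A tick box, "Taken prior to study", switches off imputation to the treatment start date and uses January and the first of the month instead. It is listed for partial dates only and supplies no year.
- **Day numbering (Section 9.5.1).** "Baseline/Treatment Start date will be referenced as Day 1 in this document".
- **Baseline steroid dose (Section 9.5.16.1).** It is the "sum of all prednisone doses over 7 consecutive days up to, but not including Day 1, divided by 7". Under Section 9.5.16, "days on which a subject does not have prednisone use recorded will be considered as 0 mg for the day", and this applies at baseline too.
- **Major efficacy analysis (Section 12.1.1).** "only subjects with a baseline average daily prednisone dose >7.5 mg/day will be included", counting steroids for SLE only.
- **Checks.** Section 9.5.16.1 compares an all-indications baseline dose with the randomization strata. Section 10.3 cross-tabulates the IXRS strata against the eCRF strata, steroid dose included.

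**The concern.** The imputed start and the baseline window do not overlap: the window closes the day before the imputed record opens. The conflict is specific to steroids. For the other allowable SLE medications, Section 9.5.18 counts a drug that starts on Day 1 and continues as baseline use, so the same imputation does no harm there.

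For a steroid marked as pre-study use, the derived baseline contradicts what the site recorded. Baseline dose then decides or feeds several things:

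- entry to the major efficacy analysis, the 25% reduction criterion and the dose covariate in its logistic model (Section 12.1.1);
- the steroid-dose subgroup for mortality and AESI (Section 8.3);
- the steroid category in the SLICC/ACR worsening model (Section 12.2.3.2);
- the baseline steroid tables (Section 10.3).

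From Day 1 the same record counts at full dose. The summary of dose category at baseline and at treatment completion (Section 12.1.1) can therefore show a rise across 7.5 mg/day that did not happen.

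**Working it through.** The RAP states no figure to reproduce on this point, so the check applies its rules to example records. The doses are illustrations.

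**Rule.** Baseline = (sum of daily prednisone-equivalent dose on Days -7 to -1) / 7. There is no Day 0 (Section 9.5.2). A record imputed to start on Day 1 covers 0 of these 7 days. A subject enters if baseline exceeds 7.5 mg/day.

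| SLE steroid records, constant dose | Actual baseline (mg/day) | Baseline under the RAP (mg/day) | Should enter | Enters under the RAP |
|---|---|---|---|---|
| 5 mg, start missing | 35/7 = 5 | 0/7 = 0 | no | no |
| 10 mg, start missing | 70/7 = 10 | 0/7 = 0 | yes | no |
| 20 mg, start missing | 140/7 = 20 | 0/7 = 0 | yes | no |
| 40 mg, start missing | 280/7 = 40 | 0/7 = 0 | yes | no |
| 5 mg, start known, plus 10 mg, start missing | 105/7 = 15 | 35/7 = 5 | yes | no |
| 10 mg, start known, plus 5 mg, start missing | 105/7 = 15 | 70/7 = 10 | yes | yes, baseline understated |

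**Response status among those who stay in.** Take 8 mg (start known) plus 5 mg (start missing), with an average of 7 mg/day in Weeks 40 to 52. The actual reduction is (13 - 7)/13 = 46%, a responder. The derived reduction is (8 - 7)/8 = 12.5%, a non-responder.

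**Does another rule rescue the record?**

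- The pre-study tick box fills month and day only, so it cannot resolve a date with no year.
- The ADPRED corticosteroid rule covers end dates.
- Section 9.4.3 allows endpoint-specific imputation, but Section 9.5.16 contains none for start dates.
- The stratum comparisons can reveal a mismatch, but no action follows from one.

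**Precision.** If a fraction f of the subjects above 7.5 mg/day is lost, the confidence interval widens by about 1/sqrt(1 - f). The documents give no f. Assumed values of 0.02, 0.05 and 0.10 give factors of 1.010, 1.026 and 1.054, that is, about 1.0%, 2.6% and 5.4% wider.

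**After the correction.** If the start is placed on or before Day -7, constant users of 10, 20 and 40 mg/day get baselines of 10, 20 and 40 and enter.

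**The case against.** The strongest reply is that the gap is narrow. It needs a start date with no day, month or year. A long-term user who remembers only the year has a partial date, and if that year precedes the treatment start year, or the tick box is checked, the rule sets 1 January, which normally falls before the window. Sites took SLE medication history at screening (protocol Section 6.1) and had to work out a steroid dose for stratification. A subject whom the site stratified above 7.5 mg/day but who is derived at or below it is discordant in both planned comparisons. The endpoint is secondary, and the imputed dates concern drugs started before randomization.

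Most of this stands, and it rules out three stronger readings that a reader might infer.

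- **That many long-term users are lost.** The documents give no count of completely missing start dates.
- **That every affected subject falls to 0 mg.** That happens only if no other SLE steroid record covers the window. One example above stays in the analysis.
- **That the treatment comparison or the primary safety results are biased.** The rule concerns pre-randomization use, so no systematic difference between arms is expected. The overall mortality and AESI differences in Sections 11.1.1 and 11.1.2 do not use baseline steroid dose.

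The reply does not show that the error would be corrected. Section 8.2 already expects steroid strata to disagree, because sites stratified on steroids for any indication while the eCRF analyses use SLE steroids. An affected subject could be put down to that cause.

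**Conclusion.** The mechanism is certain from the RAP's own rules. A completely missing start date on a steroid taken before the study contributes 0 mg to baseline, and no provision corrects it. This is a stated rule that gives a wrong value when the record is flagged as pre-study use, not merely a detail left unsaid.

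Its importance is unknown. Exclusion needs an actual dose above 7.5 mg/day, a completely missing start date, an end date on or after Day 1 or an ongoing flag, and too little dose from other SLE steroid records to keep the derived baseline above 7.5. The consequences are lost precision and misclassification in the major efficacy analysis, the steroid subgroups, the SLICC/ACR model and the baseline tables. At assumed losses of 2% to 10%, the interval widens by about 1% to 5%; the true loss may be nil. The point deserves a correction, but it gives no reason to doubt the primary safety conclusions.

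**What to change.** In Section 9.4.3 or 9.5.16.1, add a rule for SLE corticosteroid records whose start date is completely missing and whose pre-study box is checked: when ADPRED is built, treat the start as on or before the first day of the seven-day baseline window. Keep the Day 1 rule for all other records.

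Use the existing IXRS-versus-eCRF comparison by stratum (above 7.5 against 7.5 or less) to list subjects whose discordance comes from an imputed start date. A listing limited to a derived baseline of 0 would miss the subject with 5 mg known and 10 mg missing.

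The Years 2 to 5 RAP (Section 1) records unblinding of the Week 52 data on 2-JAN-2019 and completion of the statistical analysis on 7-FEB-2019, so a change now is post hoc. The practical step is to report how many records were affected. If there were none, a sentence saying so closes the point. Otherwise, re-run the major efficacy analysis with the corrected baseline and label it a sensitivity analysis.

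The cost is a short derivation rule, one listing and possibly one re-run, using a field that the RAP already names. The downside is small: a steroid begun shortly before Day 1 would be credited with a full week. For example, 20 mg/day from Day -2 has an actual average of 40/7 = 5.7 mg/day but would be given 20.

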15.4. Appendix 4: Prednisone Equivalent Conversion

- A concomitant medication is identified as a steroid if at least one associated ATC code (ATCCD1 – ATCCD6) begins with ‘H02.’
- The following routes are considered to provide systemic exposure: oral, subcutaneous, intramuscular, intradermal, and intravenous. Topical routes of administration are excluded (e.g., topical, conjunctival, intranasal).
- At data base release, all preferred terms identified with an ATC code beginning with ‘H02’ will be reviewed to ensure a conversion factor exists for all terms with a systemic route of administration.
- Similarly, all routes of administration for preferred terms with an ATC code beginning with ‘H02’ will be reviewed to ensure all systemic routes have been identified in the list above.
- In order to be converted the frequency and dose of the steroid must be present with the unit dose in milligrams (mg).
- Reported dose for systemic steroid is converted to prednisone equivalent dose using conversion factor for each particular medication (refer to online calculator <http://www.globalrph.com/corticocalc.htm>).

A two-step process will be used to calculate the prednisone equivalent daily dose:

1. $DOSE2$ (prednisone equivalent dose in mg) = $DOSE$ (collected dose in mg) x Conversion Factor
2. DD (daily dose in mg/day) = $DOSE2$ (prednisone equivalent dose in mg) x Frequency Factor

Where multiple steroids are taken on one day, the sum of these will be the prednisone equivalent daily dose. An intermediate dataset will contain the total daily prednisone equivalent daily dose for each study day. This will be used to derive prednisone endpoints.

Preferred term	Conversion factor for converting to a prednisone-equivalent dose
BETAMETHASONE	8.333
BETAMETHASONE DIPROPIONATE	8.333
BETAMETHASONE SODIUM PHOSPHATE	8.333
BETAMETHASONE VAL	8.333
BETROSPAM	8.333
CELESTONA BIFAS	8.333
CORTISONE	0.2
CORTISONE ACETATE	0.2
CRONOLEVEL	8.333
DEFLAZACORT	0.8333
DEPO-MEDROL MED LIDOKAIN	1.25
DEXAMETHASONE	6.667

Preferred term	Conversion factor for converting to a prednisone-equivalent dose
DEXAMETHASONE ACETATE	6.667
DEXAMETHASONE PHOSPHATE	6.667
DEXAMETHASONE SODIUM PHOSPHATE	6.667
FLUCORTOLONE	3
HYDROCORTISONE	0.25
HYDROCORTISONE ACETATE	0.25
HYDROCORTISONE HYDROGEN SUCCINATE	0.25
HYDROCORTISONE SODIUM SUCCINATE	0.25
MEPREDNISONE	1.25
METHYLPREDNISOLONE	1.25
METHYLPREDNISOLONE ACEP	1.25
METHYLPREDNISOLONE ACETATE	1.25
METHYLPREDNISOLONE HEMISUCCINATE	1.25

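### A one-time steroid dose with a blank or partial end date is read as a daily dose up to the imputed date, which can move a subject across 7.5 mg/day; the handling of MG/DAY records is also unsettled

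*SAP*

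**What the plan says.** All references are to the Week 52 SAP unless stated.

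- **Blank end dates (Section 9.4.3).** "For corticosteroids, the medication end date will be imputed as study completion or withdrawal date during the ADPRED dataset creation". The only stated exception is a late start: "if the start date of the medication is greater than the study completion or withdrawal date, the end date will not be imputed".
- **Partial end dates (Section 9.4.3).** With month and year known: "If the medication started prior to study withdrawal or completion set to the last day of that month". With only the year known: "if the medication started prior to study withdrawal or completion then set to 31DEC". In both cases the completion or withdrawal date is used instead when it falls in that same month or year.
- **Frequency (Appendix 4).** 'Once' has factor 1, as do OD and QD. PRN and UNK are set to null. Step 2 obtains the daily dose as "prednisone equivalent dose in mg) x Frequency Factor".
- **Units (Appendix 4).** The text requires milligrams: "In order to be converted the frequency and dose of the steroid must be present with the unit dose in milligrams (mg". The unit table nevertheless lists MG/DAY, with factor 1.
- **Use of the daily dose.** Section 9.5.16 adds up all steroid entries falling on a given day, and Appendix 4 stores one total per study day. Baseline is "the sum of all prednisone doses over 7 consecutive days up to, but not including Day 1, divided by 7" (Section 9.5.16.1). Section 12.1.1 admits subjects with baseline above 7.5 mg/day. It defines response as a reduction of at least 25% to 7.5 mg/day or less over Weeks 40 to 52.

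**The concern.** A factor of 1 is correct for a single administration when its end date equals its start date. It is wrong once an imputed end date stretches the record over several days, because the dose is then repeated on each of them. The routes in scope in Section 9.5.16 include intravenous, intramuscular and subcutaneous, so single injections are foreseeable. The frequency table treats PRN and UNK specially but does nothing comparable for 'Once'.

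The MG/DAY entry raises a second question. A dose already expressed per day should not be multiplied by a frequency again, yet step 2 has no exception. If the milligram requirement instead shuts such records out, known doses are lost.

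The daily dose decides who enters the major efficacy analysis, who responds and the baseline covariate. It also sets the steroid subgroup (Section 8.3), the steroid term in the SLICC worsening model (Section 12.2.3.2) and the cumulative dose (Section 9.5.16.3).

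**Working it through.** The plan states no figure that depends on these rules, so there is nothing to reproduce. The check applies the rules literally. Doses and dates below are assumptions for arithmetic only; conversion and frequency factors are from Appendix 4.

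**Windows.** On schedule, Week 40 is Day 281 and completion is Day 365 (Section 9.5.3). Section 9.5.16.2 sums Days 282 to 364, which is 83 days, and divides by 365 − 281 = 84.

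**Cumulative dose, blank end date.** Methylprednisolone 80 mg 'Once' on Day 141: 80 × 1.25 = 100 mg. Days 141 to 364 are 224 days, so 224 × 100 = 22,400 mg is counted instead of 100 mg.

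**Weeks 40-52, smallest dose D that breaks 7.5 on a 5 mg/day background.**
- Blank end date, start before Week 40: (5 + D) × 83/84 > 7.5, so D > 2.59 mg.
- Partial end date, 30 imputed days in the window: D > (7.5 − 5 × 83/84) × 84/30 = 7.2 mg. With 15 days, D > 14.3 mg.
- Counted once, as it should be: D > (7.5 − 5 × 83/84) × 84 = 215 mg.

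**False non-responder.** Baseline 10 mg/day, tapered to 5 from Day 200, plus triamcinolone 40 mg 'Once' (40 × 1.25 = 50 mg).
- Given on Day 150, blank end date: 55 × 83/84 = 54.35, instead of 5 × 83/84 = 4.94 mg/day.
- Given on Day 300, 30 imputed days: (415 + 1,500)/84 = 22.80, instead of (415 + 50)/84 = 5.54 mg/day.

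In both cases a responder becomes a non-responder.

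**False entrant who does not respond.** Background 5 mg/day plus the same 50 mg given once 30 days before Day 1, end date blank. Baseline is 55.0 instead of 5.0 mg/day, so the subject enters. The record also runs through Weeks 40-52, giving 54.35 mg/day and no response.

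**False responder.** This needs baseline inflated and Weeks 40-52 left alone, so it needs a partial end date. Take triamcinolone 40 mg once, dated only to the month of Day 1. By default Section 9.4.3 sets such a start date to the treatment start date, which lies outside the baseline window, so nothing is added. If 'Taken prior to study?' is checked, the start becomes the 1st of the month and the end its last day. Baseline is then up to 50 mg/day, against at most 50/7 = 7.1. With no other steroid the Weeks 40-52 mean is 0, and the subject responds unless they withdraw or add an immunomodulator.

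**MG/DAY, if multiplied.** 5 with BID gives 5 × 2 = 10; 5 with TID gives 15; 10 with QOD gives 5; 20 with QW gives 2.86. Each crosses 7.5. With QD there is no error.

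**The case against.** Several counter-arguments have force.

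- **Day-by-day expansion is inferred.** No sentence says a record is spread from start to end. The inference is strong, though: the dataset holds one total per day, and Section 9.4.3 imputes end dates so that these drugs enter the prednisone summaries.
- **'Once' is undefined.** If sites used it for once daily, factor 1 and an open end date would be right, and cutting the record to one day would create an error. The meaning must be confirmed before any change.
- **MG/DAY may be excluded.** The milligram requirement permits that reading. A reader might infer that MG/DAY doses are certainly doubled under BID; the text does not establish this. Equally, 10 MG/DAY with QOD could mean 10 mg on alternate days.
- **Safeguards exist at baseline.** Section 9.5.16.1 cross-checks an all-indication baseline dose against the randomization strata, Section 10.3 cross-tabulates the strata, and Protocol Section 10.5 describes data queries. These could reveal gross baseline errors. However, Section 8.2 already expects the steroid strata to differ, and neither strata check reaches Weeks 40-52. The Appendix 4 review asks only whether conversion factors and routes are complete. The Section 12.1.1 sensitivity analysis changes only the immunomodulator rule.
- **The endpoint is secondary.** The SAP description calls efficacy secondary in nature, and Section 8.4 applies no multiplicity control. That limits the weight of the point without removing the wrong value.

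**Conclusion.** The 'Once' defect stands on the text: a blank or partial end date turns one systemic SLE steroid dose into a daily dose up to the imputed date. It can move a subject across 7.5 mg/day at baseline or in Weeks 40-52, and it inflates cumulative dose. A blank end date usually yields a false non-responder, or a false entrant who does not respond. The MG/DAY point is an unresolved contradiction: records with a factor other than 1 are either multiplied again or left unconverted.

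Two stronger readings are tempting. One is that false entrants automatically count as responders; the working shows this needs a partial date that inflates baseline alone, and no withdrawal or added immunomodulator. The other is that the treatment difference is diluted or biased. The documents give no count of affected records, data queries may have reduced it, and the rules apply alike to both arms. The expected effect is therefore misclassification of a secondary efficacy endpoint, with size and direction not shown.

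This rests on 'Once' meaning a single administration and on records being expanded over every day from start to end.

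**What to change.** 1. In Section 9.4.3 and Appendix 4, first confirm that 'Once' means a single administration. Then, where its end date is missing or partial, set the end date equal to the start date and count the dose on one day only.
2. Reconcile the MG/DAY entry with the milligram requirement. Query MG/DAY records whose frequency factor is not 1, and do not multiply a confirmed total daily dose by frequency.
3. The RAP for Years 2 to 5 (Section 1) records that Week 52 data were unblinded on 2-JAN-2019 and the analysis completed on 7-FEB-2019, so a change before unblinding is no longer possible. Check the ADPRED code and count affected records by arm. If there are any, report the corrected major efficacy analysis as a documented sensitivity analysis. If the code already handles these records correctly, say so in the documentation.

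The cost is a few lines of text and derivation code, a record count, the MG/DAY queries, and at most one rerun of the logistic model and cumulative-dose summary. No new assessments are needed.
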